Includes the 7 days prior to departure in which the pre-travel questionnaire and a biologic (stool) specimen is collected, the full duration of travel, and through 10 days maximum post-return from travel, or until both the post-travel questionnaire and submission of the post-travel biologic (stool) specimen is complete (a maximum of 17 days post-travel)

Travel companion (group):

Two or more study participants with a common relation (friends, colleagues, or relatives) with the same itinerary, who anticipate performing the same activities during travel

Trip duration:

The number of days spent in country; excludes air travel time

Severe TD:

Hospitalization to an inpatient ward either during travel or after travel with a diagnosis of diarrhea

Acquisition of AMR gene(s):

The presence in a post-travel biologic (stool) specimen of one or more antimicrobial resistance gene(s) that were not present in a pre-travel biologic (stool) specimen from the same person, and which is known to confer antimicrobial resistance to one or more antimicrobial agents ("resistome")

Medication compliance:

Full = participant takes all scheduled doses according to directions

Good = If <15% of BSS or placebo doses were missed during travel

Fair = If 15–30% of BSS or placebo doses were missed during travel

Poor = If >30% of doses were missed during travel

Questionnaire compliance:

Full = participant completes all questionnaires

Good = participant completes >80% of all during travel questionnaires, AND
both the pre- and post-travel questionnaires

Fair = participant completes between 30–80% of all during travel
questionnaires, including AT LEAST the pre-travel questionnaire

Poor = participant completes <40% of all during travel questionnaires, and AT
LEAST the pre-travel questionnaire

Biologic (stool) specimen compliance:

Full = BOTH specimens collected and sent

Fair = ONLY one specimen collected and sent

Poor = No specimens collected and sent

Loss to follow-up:

Failure to complete the post-travel questionnaire after three attempts to contact the participant or if submission of the post-travel biologic specimen (stool) occurs more than 10 days after return from travel or is not submitted

Participant Inclusion Criteria

Willing participants must meet the inclusion criteria as outlined here:

1. Be ≥ 18 and <70 years of age at the time of enrollment

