9. Have had diarrhea (see Definitions) anytime in the previous 30 days, have diarrhea at the pre-travel consultation, or develop diarrhea before departure
10. Have been given doxycycline for malaria prophylaxis for the current trip (due to possible drug-drug interactions and decreased absorption of the doxycycline) (27)
11. Have an allergy to any component of the placebo tablets

Estimated Number of Participants

We anticipate enrolling approximately 500 participants (see Sample Size and Power Calculation).

Sample Size and Power Calculation

A sample size of 488 participants with full compliance to medications and questionnaires (244 participants in each arm) is needed to fulfill the objectives [anticipated incidence of the endpoint as 40% incidence of TD with a 30% minimum intervention protection ($0.40-[0.4 \times 0.30] = 0.28$) with an alpha of 0.05, and 80% power].

Recruitment and Enrollment

All international travelers undergo a screening questionnaire at their pre-travel consultation to determine eligibility. This short questionnaire includes questions regarding the travelers' [see **APPENDIX A**]:

1. Age
2. Travel destination(s)
3. Trip duration
4. Acute and chronic medical conditions, including diarrhea
5. Contraindications to BSS administration
6. All current medications, including antibiotic use within the 30 days before screening
7. Willingness to participate in the trial and comply with the data collection requirements

This screening questionnaire will be administered to the traveler by study personnel at The New York Center for Travel and Tropical Medicine. The purpose will be to exclude those travelers who do not meet all inclusion criteria and those who meet any exclusion criteria (see Participant Inclusion / Exclusion Criteria). Travelers who meet the inclusion criteria and do not meet any exclusion criteria will be introduced to the project objectives and procedures, including the procedures for biologic (stool) specimen collection (see Laboratory instruments).

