Participants will be asked to submit a web-based post-travel questionnaire within 10 days after return from travel, submit a biologic (stool) specimen, and provide all daily questionnaires that were completed during travel. This will be submitted via a pre-paid envelope addressed to the study clinic that was given to the participant when enrolled.

Study personnel will make follow-up telephone calls on days 3, 5, 7, and 10 after return as needed to encourage that the post-travel questionnaire, paper questionnaires from during-travel, and biologic (stool) specimens are all submitted.

The web-based post-travel questionnaire will include questions on:

1. The development of symptoms of TD since returning from abroad, including duration of symptoms
2. New antibiotic or other medication use
3. Adverse events

4. Contact with healthcare facilities or providers
5. Changes to travel itinerary during travel

Table 2. Schedule of CLINIC events (primary and secondary objectives):

	Stages			
	Pre-travel consultation (baseline)	Pre-travel (≤ 7 days before departure)	During travel	Post-travel (≤ 10 days after return)
Screening Questionnaire	X			
Informed Consent	X			
Pre-travel Questionnaire*		X		
Follow-up call(s)		X		X [†]
During travel Questionnaires			X	
Post-travel Questionnaire				X
Adverse Events Reporting			X	X

*Study personnel will call the participant to complete a pre-travel questionnaire 7 days before departure and to ensure that answers to the questions on the screening questionnaire have not changed. Reminder calls will occur as per **APPENDIX G**. If the traveler is leaving exactly 7 days after the pre-travel consultation/enrollment visit, this questionnaire can be performed at the pre-travel consultation/enrollment visit.

[†]Study personnel will call the participant within 3 days of return from travel to remind participants to complete their web-based post-travel questionnaire, submit any paper during travel questionnaires, and collect and submit the post-travel biologic (stool) sample. Reminder calls will occur as per **APPENDIX G**.

Laboratory Instruments

All participants will collect and submit a fresh biologic (stool) sample in the 7 days before departure and within 10 days after return. Participants will be

provided all instructions and materials necessary to collect and submit these samples at enrollment. All biologic (stool) specimens will be submitted by mail, and participants will be given pre-paid shipping materials.

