Headache	
Dizziness	
Ringing in your ears	
Muscle pain/soreness	
Joint pain/swelling/redness	

Drowsiness (severe)	
Confusion	
Depression	
Other (list/describe):	
Medical care	
Did you seek medical care for one or more of these symptoms? (Yes/No/Don't Know)	Y N D
→ If yes, where? (check the corresponding box(es))	...
A doctor's office	
Urgent care clinic (outpatient)	
Emergency room	
Hospital outpatient clinic setting	
Hospital inpatient ward – hospitalized	
Other (specify)	
→ Was your diagnosis travelers' diarrhea? (Yes/No/Don't Know)	Y N D
Have you started any medications in the past 24 hours? (Yes/No/Don't Know)	
→ If yes, what medication(s)?	
→ Please circle those that were provided for you at your pre-travel consultation with the study clinic.	...
What city(ies) and country(ies) have you been in during the past 24 hours? Please write answers to all questions in the corresponding box.	
Have you eaten any of the following in the past 24 hours? (Yes/No/Don't Know)	
→ Fermented or pickled foods (e.g., bean paste, fish kimchi, etc.)	Y N D
→ Yogurt	Y N D
Comments:	

Post-travel Questionnaire

PARTICIPANT UNIQUE ID: _____

GROUP ID: _____

1. Have you had any of the following symptoms since returning home from your trip (circle all that apply)?

Symptom	Duration (in days)
Fever	
Nausea	
Vomiting	
Loose stools (less than three in a 24 hour period)	
Diarrhea (three or more loose stools in 24 hours)	
Bloody diarrhea	
Constipation	
Dark or black stool	
Dark or black tongue	
Abdominal pain	
Abdominal cramps	
Fecal urgency	
Bloating	
Flatulence/gas	
Congestion/runny nose	
Sore throat	
Cough	
Rash	
Headache	
Dizziness	
Ringing in your ears	
Muscle pain/soreness	
Joint pain/swelling/redness	
Drowsiness (severe)	
Confusion	
Depression	
Other (list/describe):	
Don't know	...
I would rather not answer	...

2. Did you start taking any of the following medications since you arrived home (circle all that apply)?

- a. **Oral or intravenous (IV) antibiotics** (e.g., azithromycin [Zithromax], ciprofloxacin [Cipro], rifaximin [Xifaxan], doxycycline or minocycline, metronidazole [Flagyl], cotrimoxazole [Bactrim or Septra], penicillins [e.g., amoxicillin, Augmentin], or cephalosporins [e.g., Keflex])

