- b. **Antidiarrheals** (e.g., bismuth subsalicylate [Pepto Bismol/Kaopectate])
- c. **Antimotility agents** (e.g., loperamide [Imodium])
- d. **H2 blocker** (e.g., ranitidine [Zantac], cimetidine [Tagamet], famotidine [Pepcid])
- e. **Proton pump inhibitor** (e.g., omeprazole [Prilosec], pantoprazole [Protonix], lansoprazole [Prevacid], esomeprazole [Nexium])
- f. **Other antacids** (e.g., calcium carbonate [Tums/Rolaids], Maalox/Mylanta)
- g. **Probiotics** (*Yogurts and other fermented dairy products are probiotics. Probiotics can also take the form of capsules, pills, or powders. Probiotics also include any foods or drinks labeled as containing "live and active cultures" or "probiotics"*)
- h. **Oral or intravenous steroids** (e.g., prednisone, hydrocortisone)
- i. **Local/natural or herbal remedies** (herbs, etc.)
- j. **Other:**

3. Did you experience any of the following at any point during your travels?

Symptom	(Yes/No/Don't Know)	If yes, what was the duration (in days)?
Ringing in your ears	Y N D	
Constipation	Y N D	
Dark or black stool	Y N D	
Dark or black tongue	Y N D	
Drowsiness	Y N D	
Nausea	Y N D	
Vomiting	Y N D	
Rash	Y N D	
Other (list/describe):		

4. Did you seek medical care for an illness since returning to the United States after your trip?

- a. Yes
- b. No
- c. Don't know
- d. I would rather not answer

If yes to question 4, where did you seek and receive care?

- a. A doctor's office
- b. Urgent care clinic (outpatient)
- c. Emergency room
- d. Hospital outpatient clinical setting
- e. Hospital inpatient ward – hospitalized
- f. Other (please specify)

If yes to question 4, what was/were your diagnosis/es?

If yes to question 4, were you told that your illness was related to travel?

- a. Yes
- b. No
- c. Don't know
- d. I would rather not answer

If yes to question 4, were you told that you had travelers' diarrhea?

- a. Yes
- b. No
- c. Don't know
- d. I would rather not answer

If yes to question 4, were you told that you had a bacteria that was resistant to antibiotics?

- a. Yes
- b. No
- c. Don't know
- d. I would rather not answer

5. Did you travel to any countries not discussed during your pre-travel visit?

- a. Yes
- b. No
- c. Don't know
- d. I would rather not answer

If yes to question 5, please list the new countries you visited, the location(s) visited, and the number of days in each country:

Country name	Specific location(s) to be visited (e.g., city/town, attraction)	Number of days in this country
1.		
2.		
3.		

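### The post-travel form has no whole-trip diarrhea item, so travelers' diarrhea confined to unrecorded days has no prompted second source and may be missed

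*Combined protocol and SAP*

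**What the plan says.** The Definitions section counts as TD any diarrhea that starts after arrival in a country or within 10 days of return. Diarrhea abroad is recorded on the daily during-travel questionnaire (Appendix D), a tick-box with a 24-hour look-back.

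The post-travel questionnaire (Appendix E) has four relevant items:

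- Item 1 includes diarrhea but asks "Have you had any of the following symptoms since returning home from your trip".
- Item 2 (medications) covers only drugs started after arriving home.
- Item 3 asks "Did you experience any of the following at any point during your travels". Its rows are ringing in the ears, constipation, dark stool, dark tongue, drowsiness, nausea, vomiting, rash and a free-text other line. Diarrhea is not among them.
- Item 4 (medical care, TD diagnosis) covers only the time since return to the United States.

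The Post-travel section under Study Instruments sets the same limit: "The development of symptoms of TD since returning from abroad, including duration of symptoms".

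Missed diary days are foreseen. Good questionnaire compliance requires that the "participant completes >80% of all during travel questionnaires", together with both the pre- and post-travel forms. Missed diaries are not a criterion for removal. The sample size section states: "A sample size of 488 participants with full compliance to medications and questionnaires (244 participants in each arm) is needed to fulfill the objectives". Full compliance is defined as completing every questionnaire. On enrollment: "We anticipate enrolling approximately 500 participants".

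**The concern.** The form gives whole-trip recall for side effects but not for the primary outcome. A TD episode outside the look-back of every completed diary entry, and over before the traveler reaches home, is asked about nowhere. This covers two cases: an episode confined to missed diary days, and one falling between the last diary entry and arrival home. The second can occur even with a complete diary.

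The omission does not look like a considered rejection of recall, because item 3 already relies on it. The Procedures section also expects treatment taken abroad to be noted on the during-travel or the post-travel form, yet item 2 does not ask about it.

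For such days the analyst cannot tell absence of TD from TD that nobody recorded. If these days are treated as TD-free, cases are lost. If participants with incomplete diaries are dropped, people are excluded for a behavior that illness may influence.

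**Working it through.** **1. The plan's own figure.** Inputs from Sample Size and Power Calculation: "anticipated incidence of the endpoint as 40% incidence of TD with a 30% minimum intervention protection", so 0.40 on placebo and 0.40 × (1 − 0.30) = 0.28 on bismuth subsalicylate (BSS); and "with an alpha of 0.05, and 80% power". Sidedness is not stated; two-sided is inferred because it reproduces the stated size. With pooled variance and no continuity correction,

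n = [1.960 × √(2 × 0.34 × 0.66) + 0.842 × √(0.40 × 0.60 + 0.28 × 0.72)]² / 0.12² = (1.313 + 0.559)² / 0.0144 ≈ 243.4,

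which rounds up to 244 per arm, 488 in all. Power at 244 per arm is 80.1%. The figure reproduces exactly.

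**2. Missed days allowed under good compliance (more than 80% completed).** One in 7 (6/7 = 85.7%), two in 14 (12/14 = 85.7%), four in 21 (17/21 = 81.0%).

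**3. Equal loss of cases in both arms.** Assumptions: missed days count as no TD, and a share s of cases is captured in each arm. The documents give no value for s. The rates become 0.40s and 0.28s.

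| s | Placebo | BSS | Power at 244 per arm | Total needed for 80% |
|---|---|---|---|---|
| 1.00 | 40.0% | 28.0% | 80.1% | 488 |
| 0.95 | 38.0% | 26.6% | 77.0% | 526 |
| 0.90 | 36.0% | 25.2% | 73.7% | 570 |
| 0.80 | 32.0% | 22.4% | 66.5% | 674 |

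The risk ratio stays at 0.70. The odds ratio, which is what Table 2 of Appendix I reports, moves from 0.583 to 0.599 (s = 0.90) or 0.613 (s = 0.80).

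**4. From missed days to missed cases.** If a fraction m of days is missed independently and an episode lasts d days, the whole episode is missed with probability m^d, so s = 1 − m^d (m and d assumed).

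| m | d = 1 | d = 2 | d = 3 |
|---|---|---|---|
| 0.10 | s = 0.90, power 73.7% | 0.99, 79.5% | 0.999, 80.0% |
| 0.20 | s = 0.80, power 66.5% | 0.96, 77.6% | 0.992, 79.6% |

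A missed-day share equals a missed-case share only for one-day episodes. Missed days that cluster during illness move the loss toward the one-day column or beyond it.

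**5. Unequal capture.** With 90% captured on BSS and 100% on placebo, apparent protection is 1 − 0.252/0.40 = 37.0%. With the shares reversed it is 1 − 0.28/0.36 = 22.2%. The true value in both cases is 30%.

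**6. Analysis limited to complete diaries.** Spare participants: 500 − 488 = 12, or 12/500 = 2.4% of those enrolled, to cover incomplete questionnaires and incomplete medication together.

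**The case against.** A prospective daily diary is a defensible primary source, and the plan protects it. Each completed daily form earns $5, and good questionnaire compliance is a condition of any payment, so the fair class, which misses far more days, falls below that line. Paper forms back up poor internet access, and calls after return chase outstanding forms. An episode of more than a day can show on a neighboring diary day, item 1 catches diarrhea that persists after return, item 3 has its free-text line, and participants are told to contact the clinic about TD symptoms. Bias in Data Collection, Measurement, and Analysis warns of recall bias in the post-travel form, and Study Limitations warns that dark stool or mouth discoloration may reveal the arm and influence answers.

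All of this stands. It makes missed episodes less likely and argues against letting recall replace the diary. It does not supply a prompted question, and no text feeds the free-text line or a call to the clinic into the endpoint.

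A reader might go further and infer that the endpoint is under-counted, that protection is biased toward zero because placebo has more TD, or that the trial's real power is 66% to 74%. The documents support none of these:

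- No section says that a missed day counts as TD-free.
- More TD on placebo does not mean that a smaller share of placebo cases is captured. Equal capture leaves the risk ratio unchanged, and unequal capture can push protection either way.
- The 244 per arm are defined as fully compliant with questionnaires, so they have no missed diary day and the power losses in step 3 do not apply directly to them.

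**Conclusion.** The gap in the form is confirmed; its effect on the result is conditional. TD confined to missed diary days, or to the interval between the last entry and arrival home, has no prompted second source and may be missed. The power figures of 77%, 74% and 66% are illustrations. They rest on assumed capture shares of 95%, 90% and 80%, equal in both arms, and on missed days being scored as no TD. With days missed independently and episodes of two or three days, the loss is small even at 20% missed: about 78% and 80% power. It matters more if episodes are short or if illness itself causes missed entries, on which the documents give no data.

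Restricting the analysis to full questionnaire compliance, which the sample size section implies but no analysis section states, would avoid missed diary days. It would exchange missed cases for possible selection, with only 12 spare participants, and would leave the journey home uncovered. This is a modest weakness that touches the primary outcome and is cheap to repair.

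**What to change.** Add one row to item 3 of the post-travel questionnaire, using the diary's own definition of diarrhea and covering the time from arrival until the traveler reached home: yes, no or don't know; date of first day; duration in days.

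In the endpoint definition, keep the diary as the main source and use the recall row only for days with no diary entry, including the journey home. State how days are handled when neither source gives an answer, and which participants enter the primary analysis. Report two sensitivity analyses: diary only, and TD present if either source meets the definition.

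Cost: one form row and a few sentences, by IRB amendment. The drawbacks are recall error and answers that may be influenced by unmasking through dark stool or tongue. The diary-only analysis shows how far the result depends on them.

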To address the secondary objective, participants will also be asked to provide pre- and post-travel biologic (stool) samples for laboratory testing for the presence of gut AMR genes (see Laboratory instruments). Timing of the pre- and post-travel data and stool sample collections will be within 7 days before departure and 10 days after return from travel, respectively. Both biologic (stool) samples will be self-collected and submitted by mail to the clinic (the collection kit, and all necessary packaging and postage will be provided to the traveler). The participant will not be seen by a healthcare provider involved with the study post-travel unless they are ill and seek an evaluation.

As part of standard pre-travel consultation practices, if indicated, travelers will be prescribed anti-diarrheal medications and/or antibiotics for self-treatment of TD. These medications may include loperamide (Imodium), diphenoxylate and atropine (Lomotil), BSS (Pepto bismol), ciprofloxacin, azithromycin, or rifaximin. If these medications are taken while abroad, the travelers will be asked to note this on the during travel or post-travel questionnaires.

No difference in pre-travel advice, provision of anti-diarrheal medications, or during- or after-travel medical evaluation or advice will occur based on the traveler's assigned study arm.

Duration of Subject Involvement

The duration of each participant's involvement in the study is expected to be a maximum of 6 weeks. This will account for time to complete the pre-travel consultation/enrollment visit, 21 days (or less) of travel, and post-travel follow-up.

How the Study Design Addresses the Objectives and Hypotheses

A double-blinded, placebo-controlled randomized clinical trial is the best study design to address the study objectives and hypotheses. We aim to determine if there is a biologic benefit to an intervention (BSS administration), and a placebo-controlled methodology is required to determine if there is a statistically significant benefit of the intervention

regarding incidence of TD and acquisition of gut AMR genes. It is imperative to blind both healthcare providers and participants to ensure that biases, including selection and observer bias, are minimized.

Stakeholder Participation

The primary stakeholders for the project are international travelers, healthcare providers, and public health officials.

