Dosing will begin on the flight prior to arrival in the destination and will cease once they return home. The study medications must be taken twice daily (a morning and an evening dose); with time zone changes, the first dose should be taken to ensure that no longer than 12 hours passes before a subsequent dose.

Before departure, participants will be provided, free of charge, all needed study medication for the duration of their trip. Participants will be encouraged to take all doses of their medication and appropriately document on their daily during travel questionnaires if a dose was missed or taken off schedule.

Outcomes

The outcomes of this study will include:

	Favorable Outcome	Non-favorable Outcome
Hypothesis 1: Prevention of TD	Prevention of TD in the intervention group	TD in the intervention group at a rate similar to placebo; intervention drug side effects; adverse events

Hypothesis 2: Acquisition of AMR genes	Reduced or no presence of travel-associated gut AMR genes in the intervention group	No reduction in the presence of travel-associated gut AMR genes in the intervention group
---	---	---

The participant's study period will end in the following circumstances:

1. The traveler meets criteria for removal (see Criteria for Removal from the Study)
2. The participant voluntarily withdraws from the study (see Procedures for Implementing and Documenting Informed Consent)
3. The participant completes all study activities and submits all study questionnaires and biologic (stool) specimens
4. The participant is lost to follow-up

The participants will be instructed at enrollment to stop the study medication for any of the following reasons (although they will still be instructed to answer their questionnaires and submit biologic [stool] specimens as scheduled):

1. Antibiotics or BSS (either provided by the study personnel for TD treatment, or taken as an over-the-counter remedy) are taken for TD or for another medical condition
2. Any severe adverse events as described, such as signs and symptoms of salicylism or neurotoxicity, occur
3. Hospitalization for any reason

Barring the reasons listed above, the study medication should be taken throughout the trip duration, even if diarrhea occurs, if possible.

Criteria for Removal from the Study

Participants will be removed from the study when any of the following criteria apply:

1. Do not complete the pre-travel questionnaire (see Definitions for compliance)
2. Loss to follow-up (see Definitions)

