APPENDIX D: During-travel Questionnaire

During Travel Questionnaire

PARTICIPANT UNIQUE ID: _____

GROUP ID: _____

	Day 1	Day 2	Day 3	Day 4	Day 5
Please write the calendar date that corresponds to each day of your trip. Day 1 is your first day of arrival in the country.					
Number of tablets taken in the morning (maximum 4)					
Number of tablets taken in the afternoon/evening (maximum 4)					
Symptoms in the prior 24 hours (check off all that apply)	... 				
Fever					
Nausea					
Vomiting					
Loose stools (less than three in a 24 hour period)					
Diarrhea (three or more loose stools in 24 hours)					
Bloody diarrhea					
Constipation					
Dark or black stool					
Dark or black tongue					
Abdominal pain					
Abdominal cramps					
Urgency to relieve oneself (in reference to stool)					
Bloating					
Flatulence/gas					
Congestion/runny nose					
Sore throat					
Cough					
Rash					
Headache					
Dizziness					
Ringing in your ears					
Muscle pain/soreness					
Joint pain/swelling/redness					

Drowsiness (severe)					
Confusion					
Depression					
Other (list/describe):					
Medical care
Did you seek medical care for one or more of these symptoms? (Yes/No/Don't Know)	Y N D	Y N D	Y N D	Y N D	Y N D
→ If yes, where? (check the corresponding box(es))
A doctor's office					
Urgent care clinic (outpatient)					
Emergency room					
Hospital outpatient clinic setting					
Hospital inpatient ward – hospitalized					
Other (specify)					
→ Was your diagnosis travelers' diarrhea? (Yes/No/Don't Know)	Y N D	Y N D	Y N D	Y N D	Y N D
Have you started any medications in the past 24 hours? (Yes/No/Don't Know)	Y N D	Y N D	Y N D	Y N D	Y N D
→ If yes, what medication(s)?					
→ Please circle those that were provided for you at your pre-travel consultation with the study clinic.

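### In-trip medical care and rescue medication have structured fields only in the daily diary, so a missed diary day has no structured back-up on the post-travel form

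*Combined protocol and SAP*

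**What the plan says.** **Daily diary (Appendix D).** The care item reads "Did you seek medical care for one or more of these symptoms? (Yes/No/Don't Know" and is followed by boxes for the place of care, including an inpatient ward, and a question on whether the diagnosis was travelers' diarrhea (TD). The symptom list above it ends with an open row, "Other (list/describe", and each diary page has a comments field. The medication item is separate and carries no symptom condition: "Have you started any medications in the past 24 hours? (Yes/No/Don't Know". Tablet counts are entered morning and evening against calendar dates.

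**Post-travel form (Appendix E).** Question 2 asks "Did you start taking any of the following medications since you arrived home (circle all that apply". Question 4 asks "Did you seek medical care for an illness since returning to the United States after your trip". Question 3 does look back at the trip, asking "Did you experience any of the following at any point during your travels". It lists eight symptoms (tinnitus, constipation, dark stool, dark tongue, drowsiness, nausea, vomiting, rash) and an open row. It has no row for diarrhea, confusion, medical care or medication.

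**Protocol text.**
- Study Instruments, During Travel, item 6: the diary is to record hospital admission or provider contact abroad, with no limit to listed symptoms.
- Outcomes: the reasons to stop study medication include "Hospitalization for any reason".
- Procedures, on self-treatment drugs: "If these medications are taken while abroad, the travelers will be asked to note this on the during travel or post-travel questionnaires". The same section describes post-travel data as including medication use and medical care, without restricting them to the time after return.

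**The concern.** Two separate gaps appear when the forms are read against the protocol.

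The first is reliance on a single source. If a diary day is not completed, no later structured question asks about care or medication on that day. Two planned analyses depend on those data. Severe TD is defined by inpatient admission during or after travel with a diarrhea diagnosis, so its in-trip half comes from the diary. Hypothesis 2b(i) asks whether BSS alters gene acquisition in travelers with TD who take an antimicrobial while on BSS, so in-trip antimicrobial use is the classifying variable. A lost entry there turns a user into an apparent non-user.

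The second is scope. Even a completed diary asks about care only in connection with reported symptoms. An admission after an injury, for example, fits the stop rule under Outcomes and the description in During Travel, but nothing in the diary clearly prompts for it.

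**Working it through.** **Step 1. Which form has a structured field for which in-trip fact?**

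| In-trip fact | Diary (App. D) | Post-travel form (App. E) |
|---|---|---|
| Care or admission for a reported symptom | Yes | No; Q4 starts at return |
| Care or admission for another reason | No direct prompt; open symptom row or comments | No |
| Antibiotic, BSS or other drug started | Yes, any drug | No; Q2 starts at return |
| Selected side effects | Yes | Yes, Q3 |
| Date tablets stopped | Yes, from dated tablet counts | No |
| Reason tablets stopped | No explicit item | No |

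The second and third rows of the table, with the first, carry the point. A Severe TD admission falls in the first row: diarrhea is a listed symptom, so a completed diary captures it and only a missed day loses it. Non-symptom admissions fall in the second row and can be missed even with a complete diary.

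**Step 2. Does the next day's entry recover a skipped day?** By its wording, not reliably. Symptoms are asked for the prior 24 hours, and the medication item asks what was started in the past 24 hours. A course begun on a skipped day is not asked about again while it continues. An admission lasting several days is different, because the inpatient box can be ticked on each day.

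**Step 3. How much diary loss do the compliance definitions allow?** Under Definitions, Good questionnaire compliance is more than 80% of diary days and Fair is 30% to 80%. With completion c, the missing share is 1 − c:
- Good: below 1 − 0.80 = 20%.
- Fair: from 1 − 0.80 = 20% to 1 − 0.30 = 70%.

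Assume, for illustration, that days are missing independently of each other and of illness.
- A medication start, reportable on one day, is lost with probability 1 − c: 0.20 at c = 0.80 and 0.70 at c = 0.30.
- A three-day admission is lost only if all three days are missing, (1 − c)³: 0.20³ = 0.008 at c = 0.80 and 0.70³ = 0.343 at c = 0.30.

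If ill travelers skip consecutive days, the admission figure moves toward the one-day figure. That is plausible, but nothing in the documents quantifies it.

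**Step 4. Scale.** The point rests on no stated figure. The planned sample serves only as a denominator, and it reproduces. With 0.40 against 0.28, mean 0.34, two-sided alpha 0.05 (sidedness is not stated) and 80% power:

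n = [1.960 × √(2 × 0.34 × 0.66) + 0.842 × √(0.40 × 0.60 + 0.28 × 0.72)]² / 0.12² ≈ 243.4, rounded up to 244 per arm, 488 in total.

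Expected TD cases are 244 × 0.40 + 244 × 0.28 = 97.6 + 68.3 ≈ 166. This is the group in which hypothesis 2b(i) needs antimicrobial use classified.

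The documents give no rate of admission abroad. Assuming 0.5% to 2%, 488 participants yield 488 × 0.005 = 2.4 to 488 × 0.02 = 9.8 events. If each were reportable on a single day, expected losses would be:
- at 80% completion: 2.4 × 0.20 = 0.5 to 9.8 × 0.20 = 2.0;
- at 30% completion: 2.4 × 0.70 = 1.7 to 9.8 × 0.70 = 6.8 (6.9 from the rounded product; 9.76 × 0.70 = 6.83).

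These show sensitivity to the assumptions. They do not estimate what will happen.

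**The case against.** The case against is substantial, and much of it stands.

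- **The post-travel form does cover part of the trip.** A reader might infer that Appendix E ignores the trip altogether. It does not: question 3 asks about in-trip side effects and has free text. Only questions 1, 2 and 4 begin at return.
- **Only the care item is tied to symptoms.** A reader might take both diary items to be restricted. The medication item is not, and the symptom list is open-ended.
- **The stopping date is recorded.** A reader might infer that no form shows when tablets were stopped. Dated tablet counts show it when the diary is complete. Only the reason lacks an item.
- **There is another reporting route.** Description of Risks to the Participant and Identifying, Managing, and Reporting Adverse Events tell participants to contact study personnel about adverse events. The consent form and participant handout could not be consulted and may add instructions. The documents therefore do not support saying that serious events would simply go unrecorded.
- **The Procedures sentence on self-treatment drugs is met.** It allows either questionnaire, and the diary suffices. It is not a strict contradiction, although Appendix E offers no place for the alternative it names.
- **Diary completion is encouraged.** Each entry is paid, compensation requires at least Good questionnaire compliance, paper forms are available offline, and calls on days 3, 5, 7 and 10 after return chase missing forms.

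These points narrow the concern without closing it. Free text does not prompt for an admission or an antibiotic. The contact route depends on a sick traveler making the call. Participants are not seen after travel unless ill, and the scheduled calls are reminders. The mismatch between the symptom-limited care item and both During Travel item 6 and the Outcomes stop rule is untouched by any of them.

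**Conclusion.** The point holds in a limited form. In-trip care and rescue medication have structured fields only in the diary, the care item is narrower than two protocol statements, and the post-travel questions that could serve as back-up begin at return. Following the forms as written can lose an in-trip admission or misclassify in-trip antimicrobial use.

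The size is unknown. The compliance definitions show how much diary loss is tolerated, but actual completion, admission and rescue-medication rates are not given. The illustrative losses rest on assumed rates and on days missing at random. A claim that most serious on-treatment events will be missed would go beyond the documents.

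This is a shortfall in data capture. It does not affect the sample size or the primary TD comparison as planned, and correcting it changes no clinical rule. It is worth correcting because the change is nearly free and data that were never asked for cannot be reliably rebuilt later.

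**What to change.** In Appendix E:
1. Extend question 2 to medication started during the trip or since returning, with start dates.
2. Extend question 4 to care during the trip or since returning, for any reason, including admission, with dates and diagnosis.
3. Add one item asking whether study tablets were stopped early and why. The date can be taken from the diary counts where these are complete.

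In Appendix D, ask about medical care for any reason, not only for the symptoms listed.

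Then reconcile both appendices with Procedures, Study Instruments (During Travel) and Outcomes, so that each fact the protocol says it will collect has a field on the form named.

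The cost is three reworded items, one new item and an IRB amendment. Participants spend a minute or two longer on the post-travel form. Dates recalled after return will carry some error, so diary entries should take precedence where both exist.
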